It is estimated to take up to 1 year to recruit participants for this study. It will take approximately 3 years to complete the study and all data analyses. Participation in this study will take approximately 3-4 weeks. The length of participation is virtually identical for participants who complete Phase I and II vs. Phase II only. This is due to Phase I including about one to two hours of laboratory-based procedures prior to participants being trained and asked to use the FoodImage app to track food waste for 4 to 7 days over the subsequent week. Participants who only complete Phase II will not conduct the laboratory-based procedures but all other procedures will be identical.

Study Endpoints

The primary endpoint of this study is food waste and food waste behavior. We will explore these endpoints via the following aims and objectives:

- Development of FoodImage, a smartphone app that measures household food waste and food-waste-related behaviors; and assess differences in the accuracy, time burden of, and perceived convenience of measurements taken with the FoodImage app versus the current state-of-the-art household food waste measurement approach (a pen-and-paper diary) with and without a food scale
- Use the FoodImage app in a pilot randomized controlled trial designed to evaluate the effectiveness of reducing household food waste through behavioral nudges in the form of personalized feedback about food waste levels and household-specific reduction goals.

All data from the FoodImage app (including home address and GPS coordinates from food images) will be used as a study endpoint.

Procedures and Visit Description

The study will accomplish three activities:

- 1) Development of the FoodImage Smartphone app
- 2) Testing the FoodImage app with consumers in a lab setting (Phase I)
- 3) Randomized Controlled Trial of behavioral nudges to reduce household food waste (Phase II)

FoodImage App Development

The programming and development team that created a previous app called SmartIntake® agreed to build the FoodImage app. Originally, we expected the FoodImage app to rely on some features of the SmartIntake app, though FoodImage was ultimately built from scratch. The FoodImage app sends participants' images and accompanying data (e.g., receipts, food descriptions, Participant ID number, and timestamp) to a secure PBRC server where a team will analyze the images to estimate food waste.

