Phase II of this study is a randomized controlled trial of behavioral nudges via the FoodImage app to reduce household food waste. Phase II will occur in participants' natural environment (free-living conditions) and will include the 24 participants enrolled in Phase I and an additional 20 participants. Phase II, participants will be trained to use the FoodImage app to capture data on food purchases, food waste that occurs during food preparation, food waste that is present after eating, and food waste from food purges in free-living conditions. During data collection, subjects will record the source, reason, and destination of all food waste in the app.

Participants will use the app to collect food waste data for approximately 4 to 7 days over the first week of Phase II and these data serve as baseline data. Participants will then be provided with approximately a one-week break where they will not use the app to track food waste (or do any other study procedures). After the one-week break, participants will return to the center and will be randomly assigned (1:1 ratio) to one of the following groups:

1. Stress Management (Control Group). These participants will use the app to record food waste for approximately 4 to 7 days over the subsequent week. They will also receive information on stress management (Appendix C.1).
2. Food Saver (Intervention Group). These participants also will use the app to record food waste for approximately 4 to 7 days over the subsequent week. They will also be provided with the following:
 - a. Feedback on the amount of food waste their household created during the first week,
 - b. A goal to reduce the next week's food waste by 20% or more, and
 - c. Tips on how to reduce household food waste adapted from current consumer campaigns (e.g., Food: Too Good to Waste Implementation Guide and Toolkit, EPA 2016). This includes advice to limit purchases of unnecessary foods, donate or freeze unwanted and unspoiled foods, prioritize keeping and then eating left-overs, minimize waste during food preparation by preparing and serving smaller portions, purchase only needed foods, and purchase foods that are not near the expiration date (see Appendix C.2). A PBRC staff member will deliver tips to each respondent in this group via in-person and remote sessions (call, text, email, videoconference etc.).

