After approximately one week, the Stress Management and Food Saver groups will return to the Center to complete questionnaires about the usability of the app and, for participants who also completed Phase I, focus groups or cognitive interviews (Appendix B.3.b).

Visits

All participants in this study will complete 3 visits at Pennington Biomedical Research Center. Visit 1 will differ for participants in Phase I and Phase II. Visits 2 and 3 will be the same for participants in both Phases. Procedures are listed below.

Visit 1 (V1) – Phase I participants (Day 0)

Visit 1 will last approximately 4 hours for Phase I participants. Procedures at V1 include the following (Procedures in italic text are only completed by Phase I participants. As noted below, participants who only enroll in Phase II conduct all other non-italicized procedures.):

- Provide informed consent
- Eligibility will be verified
- *Receive training on use of the FoodImage app and pen-and-paper records, with and without use of a kitchen scale, to capture food waste data in the laboratory setting*
- *Capture data from food shopping, preparation, eating, and kitchen clean out events*
- *Complete the following questionnaires:*
 - Lifestyle and Demographics Questionnaire
 - User Preference Survey
 - PSSUQ
 - User Satisfaction Survey
- Body weight will be measured and recorded by study staff
- Height will be measured and recorded by study staff and used to calculate BMI
- Receive training on use of the FoodImage app to capture data in a free-living environment during food shopping, preparation, eating, and tossing events for approximately 4 to 7 days over the next week.

Study staff will keep in contact with participants over their free-living data collection to ensure data quality and participant compliance.

Visit 1 (V1) - Phase II participants (i.e., participants who did not enroll in Phase I) (Day 0)

Visit 1 will last approximately 2.5 hours for Phase II participants. Procedures at V1 include:

- Provide informed consent
- Eligibility will be verified
- Body weight will be measured and recorded by study staff
- Height will be measured and recorded by study staff and used to calculate BMI
- Complete the Lifestyle and Demographics Questionnaire
- Receive training on use of the FoodImage app to capture data in a free-living environment during food shopping, preparation, eating, and tossing events for approximately 4 to 7 days over the next week.

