It is hypothesized that food waste will be equivalent (within 20 grams) when measured with the app vs. direct weights of food waste, while food waste measured with the diary method will not be equivalent to directly weighed food waste. It is also hypothesized that the error from the app will be significantly smaller than error from the diary method.

Phase II analysis objectives include:

- 1) Quantifying baseline distributions for total weight of household food waste

- 2) Determining the effectiveness of the behavioral nudge in altering
 - a) Total daily weight of household food waste,
 - b) Total daily weight of each source of household food waste by occasion, including
 - i) plate waste,
 - ii) food prep waste,
 - iii) purge waste,
 - c) Total daily weight of each source of food waste by food type (e.g., dairy, meat, fruits, etc.) and by macronutrient,
 - d) Daily percent of served food that is wasted, and
 - e) Total amount of food purchased by weight and value.
- 3) Quantifying satisfaction levels with the FoodImage app as measured in Appendix B.1.a. (User Preference Survey) and Appendix B.2.c (User Satisfaction Survey),
- 4) The demographic, household and attitudinal factors measured in Appendix B.2.d (Food Environment Questionnaire) related to
 - a) Effectiveness of the behavioral nudge intervention in reducing food waste generated and all subcomponents listed above, and
 - b) Satisfaction levels with the app as measured in Appendix B.2.c (User Satisfaction Survey).

Withdrawal of Subjects

Subjects may be withdrawn from the study if they are non-compliant with study procedures and they will be notified of their withdrawal via telephone or mail. Subjects may voluntarily withdraw from the study at any time. No additional data will be collected and they will be considered drop outs in the study.

Risks to Subjects

This study involves no greater than minimal risk. The main risk is breach of confidentiality, and the PBRC team will work to minimize this during data collection, handling, and analysis.

Potential Benefits to Subjects

Participants may benefit by increased awareness of their food waste behaviors.

Setting

All research procedures will be conducted at PBRC and in participants' natural environment.

Resources Available

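### Food Saver participants record their own outcome after receiving feedback and a reduction goal, and no planned Phase II analysis examines whether the two arms record equally completely

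*Combined protocol and SAP*

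**What the plan says.** All references are to the combined protocol and SAP.

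- **Who records.** Under Phase II (Overview), "subjects will record the source, reason, and destination of all food waste in the app". Control participants record for about 4 to 7 days in the outcome week. For Food Saver the text is: "These participants also will use the app to record food waste for approximately 4 to 7 days over the subsequent week".
- **What differs between arms.** Food Saver alone receives "Feedback on the amount of food waste their household created during the first week", "A goal to reduce the next week's food waste by 20% or more", and tips on reducing waste. Control receives stress-management information.
- **Who estimates amounts.** Under FoodImage App Development, participants' images go to a server where "a team will analyze the images to estimate food waste".
- **What is analysed.** The Phase II objectives under Data Analysis and Specimen Management start the effectiveness list with "Total daily weight of household food waste" (2a). They continue with weight by source and by food type (2b, 2c), "Daily percent of served food that is wasted" (2d), and food purchased (2e). Satisfaction and related factors follow.
- **Conduct safeguards.** Under Visits, staff keep in contact during free-living collection, to support data quality and compliance; this is stated under Visit 1. Both arms have refresher app training at Visit 2 and a review of the collected data at Visit 3.
- **Where weighed waste is available.** Only in the Phase I laboratory session, before randomization to nudge or control.

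**The concern.** Staff estimate the amounts, but only from what participants choose to capture. Both arms record their own waste. The reason to record less of it, however, arises after randomization and in one arm only, so neither randomization nor baseline adjustment removes its effect. The Phase I comparison with weighed waste cannot settle the matter, because it tests the accuracy of measurement in a laboratory and not the completeness of capture at home once a target has been set.

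Phase II is meant to evaluate whether the nudge reduces household food waste. If recorded waste falls in Food Saver, the listed analyses cannot tell less waste from less complete recording, and the result would be read as effectiveness.

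**Working it through.** **No plan figure to reproduce.** Phase II has no power statement and no assumed rate of under-recording. The only stated power figures belong to Phase I.

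**1. What the objectives cover.** Objectives 2a to 2e are all outcomes. None compares completeness of recording between arms, and none varies an assumption about unrecorded waste. Contact, training and the Visit 3 review are steps in conduct, and a review of collected data does not by itself reveal waste that was never captured.

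**2. Size of the apparent effect.** Let true mean waste weight W be equal in both arms, with shares u (Food Saver) and v (control) unrecorded. Assume that capture in the baseline week was the same in both arms, which is reasonable in expectation because randomization comes later.

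Apparent reduction = 1 − W(1 − u)/[W(1 − v)] = 1 − (1 − u)/(1 − v)

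| u | v | Apparent reduction |
|---|---|---|
| 0.10 | 0 | 10% |
| 0.20 | 0 | 20% |
| 0.20 | 0.10 | 1 − 0.80/0.90 = 11% |
| 0.20 | 0.20 | 0% |
| 0.10 | 0.20 | 1 − 0.90/0.80 = −12.5% (apparent increase) |

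Only the difference between arms matters, and it could run either way. The shares are of weight, not of items.

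**3. Chance of a false positive.** Inputs: 44 participants at 1:1, so 22 per arm; two-sided alpha 0.05 (assumed for Phase II); v = 0; an unadjusted comparison of means; the same between-participant coefficient of variation (CV) in both arms. The CV and u are assumptions, since the documents give neither.

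Probability = Φ( u / [CV × √(2/22)] − 1.96 )

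| CV | u = 0.20 | u = 0.30 |
|---|---|---|
| 0.30 | 60% | 91% |
| 0.50 | 26% | 51% |
| 0.75 | 14% | 26% |
| 1.00 | 10% | 17% |

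For example, with CV 0.50 and u = 0.20: 0.20/(0.50 × 0.3015) − 1.96 = −0.63, giving 26%. A t-based calculation at u = 0.20 gives 58%, 25%, 14% and 10%. The nominal rate in that direction is 2.5%.

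**4. Whether objective 2d already protects.** Take 10 meals, each with 500 g served and 50 g left, so the true percentage is 500/5000 = 10%.

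- Two whole meals not recorded: total waste falls to 400 g (−20%), and the percentage is 400/4000 = 10%, unchanged.
- Two after-eating records omitted and counted as zero: 400/5000 = 8%, a 20% relative fall.
- The same two omitted and treated as missing: 400/4000 = 10%.

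So 2d is robust when whole meals are skipped. When only the after-eating record is omitted, it depends on a missing-data rule that the plan does not state. It does not cover preparation or purge waste.

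**The case against.** The other side has several good points.

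- **Under-recording is not shown.** A reader might infer that Food Saver participants will under-record, so that the trial is biased. The documents do not support that. They give no rate and no direction, the payment is for completing the phase, and no payment for lower waste is stated.
- **There are safeguards.** Staff contact, refresher training for both arms and the Visit 3 review are real but partial. No compliance measure from them enters the analysis.
- **Missing is not always the same as zero.** A reader might infer that unphotographed waste always looks like no waste. That fits purge and preparation waste better than plate waste, where a served-food record without an after-eating record could be identified and treated as missing.
- **Other event counts are not neutral.** The app is used to "capture data in a free-living environment during food shopping, preparation, eating, and tossing events", so it is tempting to treat all these events as measures of logging effort. The tips, however, aim at fewer purchases and smaller portions, food purchased is itself outcome 2e, and a preparation record may simply be a record of preparation waste. A working nudge could lower these counts.
- **A pass/fail rule would mislead.** It is also tempting to allow a claim of reduced waste only if logging does not fall. A household that records every meal but skips some discards would pass. The check also has little power: about 26% for a 20% difference at an assumed CV of 0.50, before baseline adjustment.

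These points limit the claim and shape the remedy. They do not supply the missing analysis.

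**Conclusion.** The concern holds as a gap in the analysis plan. Only one arm receives feedback and a goal before recording its own outcome, and no Phase II objective examines differential recording. An excess unrecorded share of 20% of waste weight in Food Saver relative to control would by itself reproduce the 20% goal; 10% would reproduce half of it. That 20% is the target given to participants, not a planned effect size. It would also be wrong to translate it into one item in five, which holds only if omitted items have average weight.

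The false-positive figures rest on assumed CVs and under-recording shares, and show a possible scale only. The appendices, including the training materials, were not in the text available. The small pilot setting moderates the point, but an effectiveness claim is still intended and the remedy is cheap.

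**What to change.** Add to the Phase II analysis, before outcome data are examined:

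1. **A descriptive logging check.** Compare the arms, adjusted for baseline and with confidence intervals, on (a) eating occasions with a served-food record per recording day and (b) the share of those occasions that also have an after-eating record. Define a recording day. Treat a served meal with no after-eating record as missing, not zero; this works only if participants also record empty plates, which the text does not state. Do not use shopping or preparation counts as logging markers, and do not make the check a gate.
2. **A tipping-point table on waste weight.** Let R be the estimated ratio of recorded waste, Food Saver to control, and e = 1 − (1 − u)/(1 − v) the excess unrecorded share. The corrected ratio is R/(1 − e). The effect disappears at e = 1 − R, and its upper confidence limit R_U reaches no effect at e = 1 − R_U. For R = 0.80, the first of these is 20%. Report both values.
3. **Wording.** State conclusions as effects on recorded food waste, read together with items 1 and 2.

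**Cost.** A little extra analysis, mostly of records the app should already hold (2d needs served food), and a more cautious claim. Selective omission of discards, especially purge and preparation waste, escapes item 1 and is addressed only by item 2.

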- 1) FoodImage, pen-and-paper records with visually estimated portion size, then pen-and-paper records with the ability to use a kitchen scale.
- 2) Pen-and-paper records with visually estimated portion size, FoodImage, then pen-and-paper records with the ability to use a kitchen scale.

Accuracy will be evaluated for both the FoodImage app and the two methods that rely on pen-and-paper records by comparing estimated food waste from these three methods to directly weighed food waste. Participants will use these three methods to estimate the amount of:

- 1) food waste that is generated when they prepare provided foods,
- 2) the resulting food portions that represents the amount of served food during a simulated meal, and
- 3) the amount of food that remains (plate waste) after the study staff discards a randomly selected amount of the served foods (participants will not eat any food).

Participants will also use all three methods to document foods from a simulated shopping trip, where participants will be provided with a grocery bag(s) of foods products and one or more receipts. It is recognized that some food products may not require use of the kitchen scale since

the packaging contains the weight or portion size of many foods. Finally, participants will also use all three methods to document foods that are to be discarded from a simulated kitchen clean out. To simulate the kitchen clean out, study staff will present to the participant a series of food products on a counter and participants will be asked to document what and how much food would be thrown away (the foods will not actually be discarded). The training materials that will be used to teach participants how to use the pen-and-paper records and FoodImage app are included in Appendix A.

Following the laboratory-procedures described above, participants in Phase I will complete questionnaires assessing their satisfaction with the FoodImage app, if they prefer to use the FoodImage app vs. a pen-and-paper record, etc. (these questionnaires are detailed below).

Phase II (Overview)

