- *User Satisfaction Survey*- This survey asks questions to help staff understand participants' satisfaction with using an iPhone app (FoodImage) to take and send photos of food waste (Appendix B.2.c).

- *Food Environment Questionnaire*- This questionnaire asks questions about purchasing food for the household (Appendix B.2.d).
- *Waste Toss Methods Questionnaire*- This questionnaire asks questions about how participants typically dispose of food in their household (Appendix B.2.e).
- *Food Waste Tip Questionnaire* – This questionnaire asks questions to help staff understand participants' satisfaction with receiving training tips to help reduce food waste (Appendix B.3.a).

Data Analysis and Specimen Management

Phase I analysis objectives include:

- 1) Determining if food waste measured with the FoodImage app is equivalent to the criterion value (directly weighed food waste) for each source (plate waste, food purges, etc.). Error (the difference between food waste measured with the FoodImage app and the criterion value) will also be quantified for each source.
- 2) Determining if food waste measured with each of the pen-and-paper diary methods (with and without a kitchen scale) is equivalent to the criterion value for each source. Error will also be quantified for each source.
- 3) Determining if the error from the FoodImage app is smaller than error from the pen-and-paper records.
- 4) Determining if satisfaction ratings differ significantly between the app and the pen-and-paper record approaches.
- 5) Determining if the amount of time respondents took to complete measurements differed between the app and diary approaches.
- 6) Qualitative assessments by respondents of the desirable and undesirable features of the app and pen-and-paper records.
- 7) Determining if the variance of waste measures differed between the app and pen-and-paper record approaches.
- 8) Assessing the accuracy of receipt data as captured by participants using the app.

Power Analysis. We base our power analysis on plate waste data gathered from previous research conducted at PBRC [20]. With an N of 24, we are powered to detect equivalence within 20 grams with power of 0.80 and alpha of 0.05. Also, *t*-tests to determine if the error from the app (weighed food waste minus estimated waste) differs significantly from the error from the diary method is powered to detect differences as small as 12.8 grams.

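### Phase I objective 7 compares the variance of recorded waste amounts instead of errors, which masks differences in precision and, if a method compresses amounts, can favour the less accurate one

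*Combined protocol and SAP*

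**What the plan says.** All references are to the combined protocol and SAP.

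- **Data Analysis and Specimen Management, Phase I objective 7:** "Determining if the variance of waste measures differed between the app and pen-and-paper record approaches". No test, breakdown by source, adjustment for the weighed value or interpretation is given.
- **Phase I objective 1** defines error separately from the measure: "Error (the difference between food waste measured with the FoodImage app and the criterion value) will also be quantified for each source". Objective 2 does the same for both pen-and-paper methods, and objective 3 compares methods on it: "Determining if the error from the FoodImage app is smaller than error from the pen-and-paper records".
- **Phase I (Overview)** provides a criterion for every method, since accuracy is judged by "comparing estimated food waste from these three methods to directly weighed food waste". The design is within-participant: "Participants will use these three methods to estimate the amount of" each kind of waste in turn.
- **Phase I (Overview), third item of the simulated meal:** plate waste is "the amount of food that remains (plate waste) after the study staff discards a randomly selected amount of the served foods".
- **Phase I (Overview), clean-out task:** "study staff will present to the participant a series of food products on a counter". Whether every participant sees the same set is not stated.

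**The concern.** Because the list uses the word error in objectives 1 to 3 and a different term in objective 7, the natural reading is that objective 7 concerns the raw recorded amounts. The variance of recorded amounts has two parts: variation in what was truly wasted, and variation due to the method. Only the second says anything about precision. The design adds to the first part for plate waste by having staff remove a random quantity.

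Two consequences follow. A real difference in precision between the app and a diary is diluted. And a diary that overstates small amounts and understates large ones produces a narrower spread of recorded amounts while being less accurate. Objective 7 is the only listed comparison of spread between methods. The t-test described in the power paragraph is on signed error and so compares average error.

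**Working it through.** **Inputs from the plan.** N = 24 in Phase I; every participant uses all methods; weighed waste is available. The plan gives no power figure for objective 7, and no SD of true waste or of error anywhere, so there is no stated figure to reproduce.

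**Assumed inputs.** App: slope 1, random-error SD 15 g. Diary: random-error SD 30 g, slope *b* (1 = no compression). Errors independent, all quantities normal. True-waste SD is varied.

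**Model.** Estimate = *b*·T + e, where T is weighed waste.

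- Variance of recorded amounts = *b*²·Var(T) + Var(e)
- Variance of error (estimate minus weighed) = (*b* − 1)²·Var(T) + Var(e)

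**No compression (*b* = 1 for both).** Error variances are 15² = 225 and 30² = 900, a ratio of 4.0 whatever the true-waste SD. For recorded amounts, Var(T) is added to both. It cancels in the difference (900 − 225 = 675 throughout) but pulls the ratio toward 1. Power is for the Pitman-Morgan paired test, two-sided 0.05, n = 24, by simulation:

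| True-waste SD (g) | Recorded variance, app / diary | Ratio | Power, recorded | Power, errors |
|---|---|---|---|---|
| 0 | 225 / 900 | 4.00 | 90% | 90% |
| 10 | 325 / 1000 | 3.08 | 76% | 90% |
| 20 | 625 / 1300 | 2.08 | 47% | 90% |
| 40 | 1825 / 2500 | 1.37 | 19% | 90% |
| 60 | 3825 / 4500 | 1.18 | 12% | 90% |
| 100 | 10225 / 10900 | 1.07 | 7 to 8% | 90% |

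True-waste variance is more than half of the app's recorded variance only when the true-waste SD exceeds the app's error SD, here 15 g.

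**With compression.** Take *b* = 0.6 for the diary and a true-waste SD of 60 g (Var(T) = 3600).

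- Recorded SD, app: √(3600 + 225) = 61.8 g
- Recorded SD, diary: √(0.36 × 3600 + 900) = 46.9 g
- Error SD, app: 15 g
- Error SD, diary: √(0.16 × 3600 + 900) = 38.4 g

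The diary looks less variable although its errors are more than twice as spread. The test on recorded amounts significantly favours the diary in about 48% of simulated trials; the test on errors favours the app in about 99%.

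**When the ranking reverses.** The diary's recorded variance falls below the app's when (1 − *b*²)·Var(T) > 675. For *b* = 0.6 that is Var(T) > 675/0.64 = 1055, an SD above about 32 g. For *b* = 0.7 it is 675/0.51 = 1324, about 36 g. For *b* = 1 it never happens.

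**Scale.** Power depends only on the ratios of the SDs. The plan's detectable difference of 12.8 g, if it refers to 80% power in a two-sided paired t-test at 0.05, implies an SD of paired error differences of about 21.4 g. The assumed SDs give √(225 + 900) = 33.5 g. Shrinking everything by 21.4/33.5 = 0.64 gives error SDs of 9.6 and 19.2 g and the same powers at true-waste SDs of about 13, 26, 38 and 64 g in place of 20, 40, 60 and 100 g.

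**The case against.** The strongest reply is that the plan does not rest its accuracy claim on objective 7. Objectives 1 and 2 quantify error by source, objective 3 compares it between methods, and the power statement and the stated hypotheses concern equivalence and error. Objective 7 carries no hypothesis, and nowhere do the documents say that a smaller variance will be read as better accuracy. This stands, and it confines the effect to one objective.

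A reader might go further than the documents allow in three ways.

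- **That objective 7 mostly reflects variation in true waste.** Without SDs this is not established. At a true-waste SD of 10 g, power on recorded amounts is still 76% under the assumptions above.
- **That true waste varies by design for every source.** Random removal is documented for plate waste only. Preparation waste may well vary because participants prepare the food themselves. If the clean-out products are identical for everyone, the two variances coincide for that source.
- **That objective 7 reverses the ranking of methods.** With slopes of 1 there is only a loss of power. Reversal needs compression together with enough true variation, and the slope of 0.6 is an illustration.

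The diary figures are also at most a picture of visual estimation. Nothing here suggests that the record kept with a kitchen scale behaves that way. Finally, the variance of recorded amounts could be of use in planning later studies, but the plan does not state that purpose.

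**Conclusion.** The point holds in a limited form. As worded, objective 7 compares a quantity that mixes true-waste variance with measurement error wherever true waste differs between participants, which is documented for plate waste. The weighed criterion that would separate the two is already collected.

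Under the assumed error SDs of 15 and 30 g with n = 24, the cost is a fall in power from 90% to about 47% at a true-waste SD of 20 g and to 7 to 8% at 100 g. There is no cost when true waste is constant. A misleading ranking arises only if a method compresses amounts. These sizes rest on assumed SDs and slopes, not on figures in the plan. The study's main accuracy comparisons under objectives 1 to 3 are not affected, so it would be wrong to conclude that the plan cannot show lower measurement error.

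**What to change.** Reword objective 7 as a comparison of the variance of error, defined as estimate minus weighed waste. Specify that it is:

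- done separately for each waste source;
- done for the app against each pen-and-paper method in turn, with and without the kitchen scale;
- tested with a method for paired variances, such as Pitman-Morgan, because the same participants supply both measures.

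Also report, for each method, the slope of the estimate on weighed waste. Error variance still contains (*b* − 1)²·Var(T) when the slope is not 1: in the example above the diary's error SD is 38.4 g against 30 g of random error. The slope is therefore needed to tell compression from random error.

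If the variance of recorded amounts is wanted for planning later studies, state that purpose and report it descriptively. The cost is a short change of wording and a little more analysis, with no new data and no added burden on participants.
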